#### **4. Study Endpoints and Covariates**

##### **4.1 Study Endpoints**

###### **Primary Endpoints:**

- Common treatment-emergent adverse events [including changes in physical examinations]
- Changes in key laboratory safety tests [albumin corrected calcium (cCalcium), phosphorus, potassium, parathyroid hormone (PTH)], ECGs and vital signs

###### **Secondary Endpoints:**

- Pharmacokinetic parameters (AUC, Cmax, tmax, t1/2) of etelcalcetide in plasma
- Pharmacodynamics: concentration of parathyroid hormone (PTH), serum calcium [total calcium, ionized calcium and albumin corrected calcium] over time
- Anti-etelcalcetide antibodies
- Incidence of treatment-emergent adverse events

##### **4.2 Planned Covariates**

Not applicable.

#### **5. Hypotheses and/or Estimations**

No hypothesis will be tested for this study. All analyses are descriptive.

#### **6. Definitions**

##### **Albumin Corrected Calcium**

The albumin corrected calcium will be calculated as

$$\text{cCa (mg/dL)} = \text{total Calcium (mg/dL)} + (4 - \text{albumin (g/dL)}) * 0.8$$

Adverse Event (AE)

**Treatment-Emergent AE (TEAE):**

A treatment-emergent adverse event is any adverse event that begins or worsens after the initial dose of investigational product (IP) and up to 30 days after the last IP administration. The severity of each adverse event will be graded using the CTCAE version 4.0. Adverse events will be coded using MedDRA version 18.1 or higher.

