### Study Design and Treatment Schema

## Study Glossary

Abbreviation or Term	Definition/Explanation
Term:	
Electronic Source Data (eSource)	source data captured initially into a permanent electronic record used for the reconstruction and evaluation of a trial.
end of study for individual subject	defined as the last day that protocol-specified procedures are conducted for an individual subject
end of treatment	defined as the last assessment for the protocol specified treatment phase of the study for an individual subject
end of study (primary completion)	defined as when the last subject is assessed or receives an intervention for the purposes of final collection of data for the primary endpoint(s).
end of study (end of trial)	defined as when the last subject is assessed or receives an intervention for evaluation in the study; if the study includes multiple parts (eg, safety follow-up or survival assessment), the end of study would include these additional parts
Source Data	information from an original record or certified copy of the original record containing patient information for use in clinical research. The information may include, but is not limited to, clinical findings, observations, or other activities in a clinical trial necessary for the reconstruction and evaluation of the trial. Source data are contained in source documents (original records or certified copies). (ICH Guideline (E6)). Examples of source data include Subject identification, Randomization identification, and Stratification Value.
study day 1	defined as the first day that protocol specified investigational product(s)/protocol-required therapies is/are administered to the subject
Abbreviation:	
ANC	absolute neutrophil count
API	Active pharmaceutical agent
ALT	alanine aminotransferase
AUC	area under the curve for plasma etelcalcetide
CaSR	calcium sensing receptor
cCa	albumin-corrected calcium
CKD	chronic kidney disease
C max	maximum plasma etelcalcetide concentration
CTCAE	Common Terminology Criteria for Adverse Events
DILI	drug induced liver injury
EAP	efficacy assessment phase
ECG	electrocardiogram
EMA	European Medicines Agency

Abbreviation or Term	Definition/Explanation
ESRD	end stage renal disease
EU	European Union
iCa	ionized calcium
ICF	informed consent form
IUD	intrauterine device
LAR	legally authorized representative
IV	intravenous
NAPRTS	North American Pediatric Renal Trials and Collaborative Studies group
PD	pharmacodynamic

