## 7.2 General Study Procedures

During the study, every effort should be made to perform the study procedures as indicated in the Schedule of Assessments ([Table 1, Section 7.1](#)). Study visits should coincide with the subject's haemodialysis (HD) schedule. Unless otherwise noted all procedures should be performed prior to HD (pre-HD). Depending on the day of the week that each subject begins the study (Day 1), Day 5 assessments may be performed on Day 6 to align with the subject's HD schedule.

Throughout the study, the permitted time windows for scheduled assessments will be as follows:

- $\pm$  15 minutes for events on Day 1
- $\pm$  30 minutes for Day 3 through 10
- +1 day for Day 5
- + 3 days for Day 30 (EOS)

Additional procedures deemed necessary as part of standard of care or as required by local laws and regulations may be performed at the Investigator's discretion.

Key assessments are described in the subsections below.

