#### **7.2.9 Physical Examination**

A physical examination will be performed by the investigator or designated physician at the time points specified in the Schedule of Assessments.

Abnormal findings found during screening will be reported on the medical history page of the CRF. Any abnormal findings or worsening findings found after the subject has received etelcalcetide will be reported on the Event CRF.

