#### **9.2              Safety Event Reporting Procedures - Adverse Events**

##### **9.2.1              Reporting Procedures for Adverse Events That Do Not Meet Serious Criteria**

The investigator is responsible for ensuring that all adverse events observed by the investigator or reported by the subject that occur after first dose of investigational product through the end of study are reported using the Event CRF.

The investigator must assign the following adverse event attributes:

- Adverse event diagnosis or syndrome(s), if known (if not known, signs or symptoms),
- Dates of onset and resolution (if resolved),
- Severity,
- Assessment of relatedness to etelcalcetide,
- Action taken.

---

The adverse event grading scale used will be the Common Terminology Criteria for Adverse Events (CTCAE) version 4.0. The grading scale used in this study is described in [Appendix A](#).

The investigator must assess whether the adverse event is possibly related to the investigational product. This relationship is indicated by a “yes” or “no” response to the question: Is there a reasonable possibility that the event may have been caused by the investigational product?

The investigator must assess whether the adverse event is possibly related to other protocol-required therapies. This relationship is indicated by a “yes” or “no” response to the question: “Is there a reasonable possibility that the event may have been caused by a study activity/procedure?”

The investigator is responsible for reviewing laboratory test results and determining whether an abnormal value in an individual study subject represents a clinically significant change from the subject’s baseline values. In general, abnormal laboratory findings without clinical significance (based on the Investigator’s judgment) are not to be recorded as adverse events. However, laboratory value changes that require treatment or adjustment in current therapy are considered adverse events. Where applicable, clinical sequelae (not the laboratory abnormality) are to be recorded as the adverse event. If the severity of an adverse event changes from the date of onset to the date of resolution, record a single event for each level of severity on the Event CRF.

The investigator is expected to follow reported adverse events until stabilization or reversibility.

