#### **9.2.2 Reporting Procedures for Serious Adverse Events**

The investigator is responsible for ensuring that all serious adverse events observed by the investigator or reported by the subject that occur after signing of the informed consent through 30 days after etelcalcetide administration are recorded in the subject’s medical record and are submitted to Amgen. All serious adverse events must be submitted to Amgen within 24 hours following the investigator’s knowledge of the event via the Event CRF.

If the electronic data capture (EDC) system is unavailable to the site staff to report the serious adverse event, the information is to be reported to Amgen via an electronic Serious Adverse Event (eSAE) Contingency Report Form within 24 hours of the investigator’s knowledge of the event. See [Appendix B](#) for a sample of the Serious

Adverse Event Worksheet /electronic Serious Adverse Event Contingency Report Form. For EDC studies where the first notification of a Serious Adverse Event is reported to Amgen via the eSerious Adverse Event Contingency Report Form, the data must be entered into the EDC system when the system is again available.

The investigator must assess whether the serious adverse event is possibly related to any study mandated activity or procedure. This relationship is indicated by a “yes” or “no” response to the question: “Is there a reasonable possibility that the event may have been caused by a study activity/procedure”?

The investigator is expected to follow reported serious adverse events until stabilization or reversibility.

New information relating to a previously reported serious adverse event must be submitted to Amgen. All new information for serious adverse events must be sent to Amgen within 24 hours following knowledge of the new information. The investigator may be asked to provide additional follow up information, which may include a discharge summary or extracts from the medical record. Information provided about the serious adverse event must be consistent with that recorded on the Event CRF.

If a subject is permanently withdrawn from protocol-required therapies because of a serious adverse event, this information must be submitted to Amgen.

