### Study Day

Post day of dose: study day= (study date - date of study Day 1) +1

Pre day of dose: study day= (study date – date of study Day 1)

The day prior to the first investigational product dosing is Day -1 while the day of the first investigational product dose is Day 1.

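### The SAP closes the treatment-emergent window on Day 31, but non-serious adverse events are collected through a final visit allowed up to Day 33, so those with onset on Day 32 or 33 are left out of the TEAE tables

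*SAP*

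**What the plan says.** **Analysis window.** SAP Section 6 counts an adverse event as treatment-emergent if it starts or gets worse after dosing and "up to 30 days after the last IP administration". The same section numbers days as "Post day of dose: study day= (study date - date of study Day 1) +1".

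**Collection window, non-serious events.** Protocol 9.2.1 makes the investigator responsible for ensuring that adverse events "that occur after first dose of investigational product through the end of study are reported using the Event CRF". The protocol glossary gives a subject's end of study as "defined as the last day that protocol-specified procedures are conducted for an individual subject". Protocol 7.2 schedules that visit for Day 30 and lets it run up to three days late, but not early.

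**Collection window, serious events.** Protocol 9.2.2 requires reporting of serious events "after signing of the informed consent through 30 days after etelcalcetide administration".

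**What happens at the final visit.** Table 1 of the protocol places the only scheduled post-dose physical examination, ECG, vital signs and full chemistry and hematology at end of study. Protocol 7.2.9 adds: "Any abnormal findings or worsening findings found after the subject has received etelcalcetide will be reported on the Event CRF".

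**Endpoint.** In both documents the first primary endpoint is common treatment-emergent adverse events, with physical-examination changes expressly included. Common means 2 or more subjects. Changes in key laboratory tests, ECGs and vital signs form a separate primary endpoint.

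**The concern.** The two windows do not end on the same day, and the gap falls on days when the final visit may legitimately take place. That visit is where a new examination finding is most likely to be recorded, because no other examination is scheduled after dosing. A finding first seen there may well be given the visit date as its onset. If that date is Day 32 or 33, the event goes onto the Event CRF as required and is then excluded by definition from the common-TEAE table and from the secondary TEAE incidence. Treatment-related events drop out too, because the SAP defines them as a subset of TEAEs, and so do the treatment-emergent events of interest named in Protocol 10.4.3.4.

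With about 10 subjects and a threshold of 2 for ‘common’, one event can decide whether a term appears in the primary table. Without a stated rule, the decision on such an event would be taken after it had been seen.

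**Working it through.** The documents give no sample size calculation or error rate, so there is no planned figure to reproduce. The check is calendar arithmetic.

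**Inputs.** One dose on Day 1. TEAE limit of 30 days after the dose (SAP 6). Study day = date minus Day 1 date, plus 1 (SAP 6). Final visit on Day 30, plus 0 to 3 days (Protocol 7.2). At least 10 subjects, at least 5 per cohort (SAP 3.2).

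**Step 1: where each window ends.** TEAE window: 30 + 1 = Day 31. Latest permitted final visit: 30 + 3 = Day 33. Gap: 33 − 31 = 2 days.

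| Final visit | Days after dose | Inside TEAE window |
|---|---|---|
| Day 30 | 29 | yes |
| Day 31 | 30 | yes |
| Day 32 | 31 | no |
| Day 33 | 32 | no |

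**Step 2: which of these days are dialysis days.** Final-visit procedures are done before haemodialysis (Protocol 7.2 and 7.2.6), so the visit should fall on a dialysis day. I assume a thrice-weekly schedule, which is what the dialysis days in Table 1 footnote a (−2, 1, 3, 5 or 6, 8, 10) imply.

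- First-of-week start: Days 1, 3, 5, 8, 10, and four weeks after the dose Days 29, 31, 33. Days 31 and 33 are available. Day −2 falls in the long gap between sessions here, which fits the footnote poorly, but the Day 5 option requires this start.
- Mid-week start: Days −2, 1, 3, 6, 8, 10, and later Days 29, 31, 34. Only Day 31 is available.
- An end-of-week start does not give a Day 3 session, so it does not fit the schedule.

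Day 30 itself is not a dialysis day under either fitting pattern, so the tolerance would be used routinely. The next session, Day 31, is inside the window. Only a Day 33 visit after a first-of-week start is outside it.

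**Step 3: what one lost event does.** With 10 subjects, a term seen in two has 2/10 = 20%. Excluding one leaves 1/10 = 10%, below the 2-subject threshold, so the term leaves the common-TEAE table. In a cohort of 5, one subject is 1/5 = 20 percentage points.

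**Step 4: how often a late visit might occur.** The documents give no figure. If each of 10 subjects independently has probability q of a Day 32 or 33 visit, the chance of at least one such visit is 1 − (1 − q)^10: 0.401 for q = 0.05, 0.651 for q = 0.10 and 0.944 for q = 0.25. These are chances of a late visit only. A non-serious event must also be recorded as starting or worsening on those days.

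**The case against.** Four arguments favour leaving the SAP as it is.

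**Thirty days follows the protocol.** The design section describes safety follow-up up to 30 days after dosing, and required serious-event reporting stops there too. The protocol never defines treatment-emergent. This stands as far as it goes: the 30-day figure may be deliberate, and a reader who infers that the no-changes statement in SAP Section 11 is wrong goes further than the documents allow. It does not reconcile the SAP with the longer collection period for non-serious events.

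**Most data from a late visit are kept.** A reader might infer that everything found at such a visit is lost from the primary endpoint. It is not. Laboratory, ECG and vital-sign values are summarised by scheduled time point with no 30-day cut (SAP 10.1 and 10.5.2 to 10.5.4), and the maximum QTc categories use unscheduled values as well. The TEAE rule turns on onset or worsening, not discovery, so a finding made on Day 33 that began by Day 31 still counts. Under SAP Appendix B, an entirely missing start date with a missing or post-dose stop date is set to the dose date, so that event also stays in. Excluded events remain in the listing (SAP 10.6.4). All of this stands.

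**Half the permitted days is not half the visits.** Two of four calendar days lie outside the window, but step 2 shows that dialysis scheduling leaves mainly Day 33, for one start pattern. This stands.

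**Late events are unlikely to be drug effects.** The effective half-life in adults on repeated dosing is given as 3 to 5 days (Protocol 2.2.2), so Day 32 is about 31/5 = 6 to 31/3 = 10 half-lives after the dose. That lowers the clinical weight. However, treatment emergence is defined by time and not by cause, and events on Day 31 are counted at practically the same distance from dosing.

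**Conclusion.** The mismatch is real and minor. The TEAE window ends on Day 31, and collection of non-serious adverse events can run to Day 33. What is lost from the common-TEAE primary endpoint and the TEAE incidence tables is a non-serious event, including a physical-examination finding, whose recorded onset or worsening is on Day 32 or 33. Serious events on those days fall outside the required reporting period in any case.

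If visits follow thrice-weekly dialysis, the exposure is mainly a Day 33 final visit after a first-of-week start. Subjects on other schedules could also have a Day 32 visit. The documents do not say how many late visits to expect, so no expected number of lost events can be given. The study is descriptive and no test is affected. The consequence that can be shown is that one event can take a term from 2 of 10 subjects to 1 of 10 and so out of the common table.

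**What to change.** In SAP Section 6, define a TEAE as any adverse event that begins or worsens after the dose and up to the later of (a) 30 days after the dose and (b) the subject's end-of-study date, which the SAP already takes from the End of Study CRF page.

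The words ‘the later of’ matter. A window that simply ended at the final visit would drop a Day 31 event after a Day 30 visit. It would also drop events, including serious ones, that occur within 30 days of the dose in a subject who left early. With the later date, no event now counted is lost and all four permitted visit days fall inside the window.

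The cost is one sentence, with no new data or visits. The window becomes up to 2 days longer for some subjects whose visits are within tolerance, so its length varies slightly. A short note should say that required serious-event reporting still ends 30 days after the dose. The change should be made before database lock, so that it is not decided in the light of a particular event.

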**Adverse Events of Interest (EOI):**

Adverse Events of Interest are: convulsions, hypersensitivity, hypocalcemia, hypophosphatemia, infusion reaction, Torsade de pointes-QT prolongation and ventricular tachyarrhythmias . Unless otherwise specified, the narrow search scope will be used for all EOIs.

**Common Treatment-Emergent AE:**

Common treatment-emergent adverse events include those with occurrence in 2 or more subjects.

**Serious Adverse Event:**

Refer to Section 9.1.2 of the protocol for the definition of serious adverse event.

**Treatment-Related AE:**

A treatment-related AE is any treatment-emergent AE that per investigator's review has a reasonable possibility of being caused by the investigational product.

Baseline

For any variable, unless otherwise defined, baseline is the last assessment taken prior to the first investigational product administration.

Baseline iPTH, cCa, total calcium, ionized calcium are defined as the average of screening and Day -2 assessments. If not all the values are available, the average will be calculated based on available value(s).

Baseline pre-dialysis ECG parameters including PR, QRS, QT, QTcB and QTcF are defined as the average of last non-missing pre-dialysis screening assessment and Study Day -2 pre-dialysis assessment.

---

The use of concomitant medication of interest at baseline is defined as use of each concomitant medication on Study Day 1. This includes medication use that starts prior to Study Day 1 and ends on Study Day 1 or duration of use covers Study Day 1.

Change from Baseline

The arithmetic difference between a post-baseline value and the baseline value:

Change (absolute) from Baseline = (Post-baseline Value – Baseline Value)

Percent change from Baseline

Percent Change from Baseline = [(Post-baseline Value – Baseline Value) / Baseline Value] x 100

Body Mass Index (BMI)

BMI will be calculated as weight (kg)/ [height (m)] in the clinical database.

Corrected (Bazett) QT Interval (QTcB)

The Bazett correction will be calculated from the investigator reported QT (msec) and RR interval (msec) (QTcB=QT/(RR/1000)0.50).

Corrected (Fridericia) QT Interval (QTcF)

The Fridericia correction will be calculated from the investigator reported QT (msec) and RR interval (msec) (QTcF=QT/(RR/1000)0.33).

End-of-Study

The EOS is the last planned clinical visit for each subject enrolled in this study. The last planned visit day for subjects in cohort 1 and 2 is on Study Day 30.

Subject-level End of Study (EOS) Date

End of study for each subject is defined as the date the subject last participated in the study. The date will be recorded on the End of Study CRF page.

Enrollment

A subject will be considered enrolled when the Investigator decides that the subject has met all eligibility criteria. Enrollment Date is defined as the date collected on the CRF.

Investigational Product

The term investigational product is used in reference to etelcalcetide.

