#### **6.4 Concomitant Therapy**

Throughout the study, investigators may prescribe any concomitant medications or treatments deemed necessary to provide adequate supportive care except for those listed in [Section 6.7](#).

An attempt should be made not to change the subjects' treatment during the course of the study as long as, in the judgment of the investigator, the subjects' safety is not jeopardized. All use of concomitant medications and supplements will be recorded on the applicable CRF. Concomitant therapies are to be collected from informed consent through the end of safety follow-up period. Collect therapy name, indication, dose, unit, frequency, route, and start date and stop date.

In cases of symptomatic hypocalcemia or if the serum calcium level is less than 7.5 mg/dL (1.875 mmol/L), oral or IV calcium will be administered as necessary.

All herbal supplements, vitamins, and nutritional supplements taken within the last 30 days prior to dosing on Day 1 (and continued use, if appropriate) must be reviewed and approved by the Principal Investigator and Amgen Medical Monitor.

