#### 7.2.4 Treatment

The following procedures will be completed during the treatment period at the times designated in the Schedule of Assessments ([Table 1](#)). On Day 1 etelcalcetide is to be administered after the completion of all required pre-dose assessments and after HD, during rinse back. Subjects will remain in the clinical research unit for observation until the 4 hour PK sample is collected.

- Etelcalcetide administration
- PK (10 min and 4 hour post dose)
- Laboratory assessments (pre-HD)
- Serious Adverse Event reporting
- Adverse Event reporting
- Documentation of concomitant medications

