### Screening Date

Screening date is defined as the date of screening assessment.

### Study Day 1

Day 1 is defined as the day that investigational product is administered to the subject.

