##### **10.7.2 Exposure to Concomitant Medication**

All medications will be coded using the World Health Organisation Drug (WHO DRUG) dictionary. A subject listing of concomitant medications during the study will be presented.

The count and percentage of subjects receiving the following selected medications: nutritional vitamin D (vitamin D supplement), vitamin D sterol (active vitamin D), calcium supplements, and phosphate binder will be summarized by cohort and overall at baseline and during the study.

The number and proportion of subjects with each dialysate calcium concentration at baseline will be summarized. Summary of changes in dialysate calcium concentration during the study will be provided if data allows.

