### Imputation Rules for Partial or Missing Start Dates

		Stop Date						
		Complete: yyyymmdd		Partial: yyyy-mm		Partial: yyyy		Missing
Start Date		<1 st Dose	≥1 st Dose	<1 st Dose yyyy-mm	≥1 st Dose yyyy-mm	<1 st Dose yyyy	≥1 st Dose yyyy	
Partial: yyyy-mm	=1 st Dose yyyy-mm	2	1	2	1	N/A	1	1
	≠ 1 st Dose yyyy-mm		2		2	2	2	2
Partial: yyyy	=1 st Dose yyyy	3	1	3	1	N/A	1	1
	≠ 1 st Dose yyyy		3		3	3	3	3
Missing		4	1	4	1	4	1	1

1 = Impute the date of first dose

2 = Impute the first of the month

3 = Impute January 1 of the year

4 = Impute January 1 of the stop year

Note: For subjects who were never treated (first dose date is missing), partial start dates will be set to the first day of the partial month.

Note: If the start date imputation leads to a start date that is after the stop date, then do not impute the start date.

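### SAP Section 6 lets calcium first given after the dose on Study Day 1 count as baseline use, and Appendix B can do the same for some later starts with incomplete dates

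*SAP*

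**What the plan says.** SAP Section 6 (Definitions, Baseline) gives medications of interest their own baseline rule: "The use of concomitant medication of interest at baseline is defined as use of each concomitant medication on Study Day 1". The next sentence adds: "This includes medication use that starts prior to Study Day 1 and ends on Study Day 1 or duration of use covers Study Day 1". The same section fixes the day: "Day 1 is defined as the day that investigational product is administered to the subject".

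Calcium supplements are on the list of medications of interest, with nutritional vitamin D, active vitamin D and phosphate binders. SAP 10.7.2 says that the number and percentage of subjects receiving each "will be summarized by cohort and overall at baseline and during the study".

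SAP 9.3 sends incomplete concomitant medication dates to Appendix B, where one of the start-date codes reads "1 = Impute the date of first dose".

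On the clinical side, Protocol 6.4 provides that, for symptomatic hypocalcaemia or a calcium value below its stated threshold, "oral or IV calcium will be administered as necessary". The fields it lists for concomitant therapy include indication, dose, route, start date and stop date, but no clock time. Protocol 7.2.4 places the dose after haemodialysis on Day 1 and continues: "Subjects will remain in the clinical research unit for observation until the 4 hour PK sample is collected". Table 1 schedules a calcium sample at that 4-hour point.

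**The concern.** Hypocalcaemia is the risk that the protocol ranks highest, and SAP 10.7.2 is the only planned summary table of calcium and vitamin D use. A reader will set its baseline column against its during-study column to see whether children needed calcium after the drug. That comparison works only if the baseline column holds therapy that was in place before the dose.

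The definition is tied to a calendar day rather than to the dose, and part of that day falls after the dose, including an observation period with a calcium measurement. The imputation code can then place some later starts on the same day. Setting an unknown start to the dosing date is cautious for adverse events, because it makes them treatment-emergent. Combined with a Day 1 baseline rule, it works the other way for medications.

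**Working it through.** The plan gives no figure to reproduce. The check reads the rules together and then sizes the effect.

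**1. Start on Day 1, complete dates.** Suppose calcium is first given after the dose on Day 1. It is used on Study Day 1, so the first sentence of the rule is met. The second sentence opens with an inclusion and lists cases; it does not exclude a Day 1 start. No clock time is among the listed fields, so dates alone cannot separate a start before the dose from one after it. Every such course can be counted as baseline use.

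**2. Later start, incomplete date.** Reading the Appendix B grid for a stop date on or after first dose, or missing:

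- start month equals the dosing month: code 1, dosing date
- start year equals the dosing year, month unknown: code 1, dosing date
- start missing: code 1, dosing date
- start month differs from the dosing month: code 2, first of that month, which for a later month is after dosing and so not baseline
- start year differs from the dosing year, month unknown: code 3, January 1 of that year, which for a later year is not baseline

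**3. How often code 1 would catch a post-dose start, given that the date is incomplete.** Assumptions, not in the documents: the dosing date is uniform over a 365-day year and the start day is uniform over the window. Let j be days after dosing, so Day 2 is j = 1. There are 365 × 9 = 3,285 date pairs for Days 2–10 and 365 × 29 = 10,585 for Days 2–30. The sums of j are 45 and 435.

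- Year only: pairs that cross the year end escape. 1 − 45/3,285 = 98.6%; 1 − 435/10,585 = 95.9%.
- Month and year, Days 2–10: 45 pairs escape at each of 12 month ends. 1 − 540/3,285 = 83.6%.
- Month and year, Days 2–30: pairs that stay in the month are 31 × 29 − 435 = 464 for a 31-day month, 30 × 29 − 435 = 435 for a 30-day month, and 27 × 28/2 = 378 for a 28-day month. (7 × 464 + 4 × 435 + 378)/10,585 = 5,366/10,585 = 50.7%.

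| Start date recorded as | Start on Days 2–10 | Start on Days 2–30 |
|---|---|---|
| Complete | 0% | 0% |
| Month and year | 83.6% | 50.7% |
| Year only | 98.6% | 95.9% |
| Missing | 100% | 100% |

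**4. Effect on the table.** SAP 3.2 plans at least 5 subjects per cohort and at least 10 in all. One extra baseline count is 1/5 = 20 points in a cohort of 5 and 1/10 = 10 points in 10 subjects.

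As an illustration, assume 5 subjects, 2 on calcium before dosing and 1 first given it after the dose on Day 1. Correctly classed, baseline is 2/5 = 40% and during-study 3/5 = 60%, a difference of 20 points. With the Day 1 start also counted at baseline, both columns read 3/5 = 60% and the difference is 0. This takes the during-study column to mean any use after dosing; the SAP does not define that period.

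**The case against.** **The second sentence of the rule points to background therapy.** Both of its cases read naturally as use carried into Day 1, and that may be all that was intended. This stands as a likely intention, but the text does not exclude a Day 1 start.

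**There is no conflict with the general baseline rule.** A reader might infer one, because elsewhere in Section 6 "baseline is the last assessment taken prior to the first investigational product administration". That rule applies only where nothing else is defined, and medication use is defined separately. The objection stands in full.

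**Rescue treatment is not moved out of the study period.** A reader might infer that a treated child disappears from the during-study column. Nothing in SAP 10.7.2 does that; the child gains a baseline count.

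**The safety signal has other routes.** Protocol 9.2.1 makes laboratory changes that need treatment adverse events, and Protocol 9.2.2.2 sets reporting rules for calcium reductions. SAP 10.5.2 tabulates low corrected calcium at four cut-offs, SAP 10.6.4 tabulates hypocalcaemia as an event of interest, and SAP 10.7.2 lists every concomitant medication by subject. With about 10 children those listings can be read line by line. It would be wrong to conclude that treated hypocalcaemia would go unseen.

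**The imputation route is narrow, and often right.** It needs an incomplete start date for a drug begun during a short study with frequent visits, and the documents give no rate for that. For a long-standing drug with an unknown start, code 1 plus the Day 1 rule gives the correct answer, so the fix must not simply drop such drugs.

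**Coding is unknown.** Whether rescue calcium, especially IV, is classed as a calcium supplement depends on the case report form, which is not in the documents.

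**Conclusion.** The point holds as a misclassification that the stated rules permit in one descriptive table. Calcium first given after dosing on Day 1 can be counted as baseline use even with complete dates. A later start can be counted the same way only when Appendix B code 1 applies. The cost is a baseline percentage that is too high by 20 points per affected subject in a cohort of 5, and a baseline-to-study comparison that can show no change when use was new.

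This rests on three things: that calcium is actually given after dosing, that it is classed as a calcium supplement, and that the programmer follows the first sentence of the rule literally. The documents give no probability for any of them. The percentages for incomplete dates are conditional on such a date and on the uniform-date assumptions; they are not expected error rates. The point concerns tabulation only and says nothing about when calcium should be given.

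**What to change.** - **SAP Section 6.** Define baseline use of a medication of interest as started before Study Day 1 and not stopped before dosing. A stop date on Day 1 would still qualify, as the SAP already intends.
- **Incomplete start dates.** Do not use a start date imputed to the dosing date to assign baseline status. Assign it from the recorded indication and, where the record shows it, from documented use before dosing. Appendix B itself can stay as it is for other purposes.
- **SAP 10.7.2.** Add a row, by cohort and overall, for subjects with a new start or a dose increase after dosing. This also covers the child already on a drug, for whom an any-use count could not show an increase.

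If starts imputed to the dosing date are not treated as prior starts, the share of post-dose courses (Days 1–30) counted as baseline in the check above falls to 0% for every type of incomplete date.

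The cost is SAP wording and one table row; indication, dose and dates are already collected under Protocol 6.4. There are two drawbacks. A drug truly started on Day 1 before the dose would count as post-dose. A background drug with an incomplete date could be missed if its indication and prior use are not clear, since medications are documented at screening and Day -2 but the Protocol 6.4 field list has no visit field.
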